### 5.6.4.2 Electrocardiogram

An ECG will be performed at Visit 1 (screening), Visit 2 (Day 1), Visit 3, Visit 4, Visit 6, Visit 8 (end of treatment) and Visit 9 (end of taper).

Summaries will be presented by treatment group for ventricular rate, PR interval, QRS duration, QT interval and QTcB, at each visit. Change from baseline to each post-baseline visit will also be presented.

A separate table will be produced, by treatment group and visit, presenting the incidence of patients with an ECG indicative of a medical condition at Visit 1 and indicative of an AE after Visit 1.

Based on the criteria presented in Section 8, defined flagged values will be identified at each visit. The number of patients with at least one post-baseline flagged ECG parameter value will be summarized by parameter, flagged criteria and treatment group.

### 5.6.4.3 Physical Examination

A physical examination will be performed at Visit 1 (screening), Visit 2 (Day 1), Visit 3, Visit 4, Visit 6, Visit 8 (end of treatment) and Visit 9 (end of taper).

Any relevant findings at screening are included as part of the patient's medical history. Any changes seen after screening that are indicative of an AE are to be recorded as such on the AE form and included as part of the AE summaries.

Additionally, height and weight are recorded as part of the physical examination. Height and weight will be summarized and listed together with the vital signs parameters.

Incidence of patients with a physical examination indicative of a medical condition at Visit 1 and indicative of an AE after Visit 1 will be summarized by treatment group and visit.

---

#### 5.6.4.4 Columbia-Suicide Severity Rating Scale (Children's)

The C-SSRS is completed at Visit 1 (screening), Visit 2 (Day 1), Visit 3, Visit 4, Visit 6, Visit 8 (end of treatment) and Visit 9 (end of taper), for patients who are 6 years and older and capable of understanding and answering the questions, in the investigator's opinion. Questions are asked on suicidal behavior, suicidal ideation and intensity of ideation. At the screening visit, questions are in relation to lifetime experiences and all subsequent questioning in relation to the last assessment.

The following C-SSRS data will be summarized by treatment group at each visit for patients in the safety analysis set:

- Incidence of the following suicidal ideation:
  - Wish to be dead.
  - Non-specific active suicidal thoughts.
  - Active suicidal ideation with any methods (not plan) without intent to act.
  - Active suicidal ideation with some intent to act, without specific plan.
  - Active suicidal ideation with specific plan and intent.
- Incidence of the following suicidal behavior:
  - Actual attempt.
  - Interrupted attempt.
  - Aborted attempt.
  - Preparatory acts or behavior.
  - Suicidal behavior.
  - Completed suicide.

In addition, the number of patients with any suicidality, any suicidal ideation and any suicidal behavior will be summarized by treatment group at screening, baseline and at any time post-baseline. Suicidality is defined as at least one occurrence of suicidal behavior or suicidal ideation.

The number of patients experiencing the following, at any time post-baseline, will also be summarized:

- Complete suicidality.
- Emergence of suicidal ideation.
- Worsening of suicidal ideation.
- Emergence of suicidal behavior.

Emergence of suicidal ideation is defined as having no suicidal ideation at baseline and having reported any type of suicidal ideation at any time post-baseline. Worsening of suicidal ideation is defined to occur when the most severe suicidal ideation rating at any time post-baseline is more severe than its rating at baseline. Emergence of suicidal behavior is defined as having no suicidal behavior at baseline and reporting any type of suicidal behavior at any time post-baseline. If the C-SSRS was not completed at screening or baseline then the patient will not be included in summaries of emergence or worsening of suicidal ideation or behavior.

#### **5.6.4.5 Growth and Development**

IGF-1 levels will be analyzed as part of the clinical laboratory testing. IGF-1 levels will be summarized on a continuous scale, including change from baseline, by treatment group.

Change from baseline to the end of treatment visit for IGF-1 levels will also be plotted against the Tanner Stages, weight, and height recorded at baseline.

The pubic hair growth (both sexes), genital (males only) and breast (females only) development of all adolescent patients (i.e., 10 to less than 18 years of age at the time of signing the informed consent form, or earlier if clinically indicated by onset of menarche or other signs of precocious puberty) will be assessed using Tanner Staging. The patients will undergo a discreet physical examination and be assigned a value under each category of Pubic Hair Growth (both sexes), Genitals (male patients only), and Breasts (female patients only).

Patients will be examined at Visit 2 (Day 1) and Visit 8 (end of treatment). Once a patient reaches a score of V (i.e., 5) the examination need not be performed again.

Tanner Stages will be summarized on a categorical scale, by treatment group.

#### **5.6.4.6 Menstruation**

Caregivers will be asked if the female patient is menstruating and details will be recorded as part of their medical history (Visit 2); any changes in normal cycles will be captured at Visit 8 (end of treatment).

Menstruation details will be summarized as appropriate, including any changes in normal cycles at the end of treatment, by treatment group.

#### **5.6.4.7 Cannabis Withdrawal Scale (18 Years)**

The CWS is a 19-item scale with each item (withdrawal symptom) measured on a 0–10 NRS (0 = Not at all; 5 = Moderately; 10 = Extremely). The patient or their caregiver is asked to record the extent to which each withdrawal symptom was experienced in the last 24 hours and also to rate the negative impact on normal daily activities (i.e., 2 separate scores are recorded for each item using the same 0–10 NRS). Scores are calculated as the sum of the 19 items for each measure, i.e., each separate score has a theoretical maximum of 190.

The CWS will be used at Visit 2, to establish a baseline score, and then again at Visit 9, the safety follow-up telephone call on Day 123 and Visit 10 for any patient completing the study or withdrawing early. Patients entering the OLE on the day of Visit 8 will continue taking IMP; in this instance withdrawal will be evaluated at the end of their participation in the OLE.

The 2 derived scores, recorded at each visit, will be summarized, on a continuous scale, by treatment group. The change from baseline (Visit 2) will also be included.

If any of the individual items are missing, for each measure, then the corresponding derived score will not be calculated.

The summary will be presented separately for all patients with a completed scale and patients 18 years of age.

#### **5.6.4.8 Pediatric Cannabinoid Withdrawal Scale (4–17 Years)**

The PCWS was developed from the 19-item validated CWS (adults) that assesses mood, behavioral and physical symptoms associated with cannabis, which was based on the Marijuana Withdrawal Checklist. The modified 10-item PCWS was developed from a low

literacy version of the CWS. Symptoms specific to adult cannabis withdrawal have been removed and the wording has been amended to be comprehensible to children of the specified age range.

Ratings are based on a 4-point scale where 0 = none, 1 = a little bit, 2 = quite a bit, and 3 = a lot. This rating scale has been compacted from the original 11-point Likert scale used for the CWS in order to simplify the range of options to consider for potential intellectually disabled children. The PCWS was designed with epileptic children in mind as a tool to assess the safety of cannabinoid medications with respect to the stimulation of cannabinoid withdrawal syndrome when medications are withdrawn. As there may be a wide range of intellectual or developmental difficulties in severely epileptic children, from no intellectual or developmental impairment to extreme, the PCWS has been designed to be administered by a treating clinician, either directly to the child, or to the parent or caregiver of the child, reflecting on the child's symptoms within the chosen timeframe.

A derived score is calculated as the sum of the 10 items and has a theoretical maximum score of 30.

The PCWS will be used at Visit 2, to establish a baseline score, and then again at Visit 9, the safety follow-up telephone call on Day 123 and Visit 10 for any patient completing the study or withdrawing early. Patients entering the OLE on the day of Visit 8 will continue taking IMP; in this instance withdrawal will be evaluated at the end of their participation in the OLE.

The derived score, recorded at each visit, will be summarized, on a continuous scale, by treatment group. The change from baseline (Visit 2) will also be included.

If any of the individual items are missing, then the derived score will not be calculated.

The summary will be presented separately for all patients with a completed scale and patients 4–17 years of age.

## **5.7 Other Measures**

### **5.7.1 Concomitant Medication**

Medications will be coded using the World Health Organization Drug Dictionary, Version June 2014.

A medication will be considered concomitant if it has a start date on or after the first dose of IMP or if it was started prior to the first dose of IMP and was ongoing. If a medication has a partial or missing start/stop date and it is unclear from the date whether the medication was taken after the first dose of IMP then it will be considered concomitant.

For summaries and listings of medications the following approach will be used to determine the Anatomical Therapeutic Chemical (ATC) term to be presented:

- If coded to level 4 then the level 4 coded term will be presented.
- If coding is not performed at level 4 but level 3 coding is present then level 3 coded term will be presented.
- If coding is not performed at level 3 but level 2 coding is present then the level 2 coded term will be presented.
- If coding is not performed at level 2 but level 1 coding is present then the level 1 coded term will be presented.

Summaries of each of the following by ATC term and preferred term will be summarized by absolute counts (n) and percentages (%):

- History of antiepileptic medications;
- Concomitant antiepileptic medications;
- Concomitant rescue medications; and
- Other concomitant medications.

The ATC term, preferred term, reported generic name and reported brand name will be listed.

An additional summary table will be produced for concomitant antiepileptic therapies, displaying the number and percentage of patients with a vagus nerve stimulation device or on a ketogenic diet.

The start day and stop day will be included in the listing according to Section 5.1.2. If the date is partial and the exact day is unknown then the text 'pre' or 'post' will replace the start or stop day if it is clear from the partial date that the medication started or stopped prior to or after the first dose of IMP.

### **5.7.2 Plasma Concentrations of Concomitant Antiepileptic Drugs**

Blood sampling for AEDs will be performed at Visit 2 (Day 1), Visit 4, Visit 6 and Visit 8 (end of treatment). For each AED, plasma concentrations will be summarized by treatment group at each visit for patients in the safety analysis set.

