
Statistical Considerations
	
The following endpoints will be described and compared between treatment groups, using appropriate statistical methods, over the 14-week, double-blind treatment period:
 
 
• Change in total convulsive seizure frequency.
 
• Number of patients experiencing a >25% worsening, -25 to +25% no change, 25–50% improvement, 50–75% improvement or >75% improvement in convulsive seizures from baseline.
 
• Number of patients considered treatment responders, defined as those with a <math>\geq 25\%</math>, <math>\geq 50\%</math> or <math>\geq 75\%</math> reduction in convulsive seizures from baseline (overall and four-weekly).
 
• Number of patients who are convulsive seizure free.
 
• Change in non-convulsive seizure frequency.
 
• Change in total seizure frequency.
 
• Change in subtypes of seizures.
 
• Changes from baseline in number of episodes of status epilepticus.
 
• Changes from baseline in duration of seizure subtypes as assessed by the CGICSD.
 
• Change from baseline in use of rescue medication.
 
• Changes from baseline in number of inpatient hospitalizations due to epilepsy.
 
• Changes from baseline in Sleep Disruption 0–10 NRS score.
 

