	
 
• Changes from baseline in EDSS score.
 
• Changes from baseline in QOLCE score.
 
• Change from baseline in cognitive assessment battery.
 
• Changes from baseline in Vineland-II score.
 
• Change from baseline in growth and development by measurement of height, weight, IGF-1 levels and Tanner Staging (for patients aged 10–17 [inclusive], or earlier if clinically indicated by onset of menarche or other signs of precocious puberty).
 
• Changes from baseline in the CGIC score.
 
• Plasma and urine concentrations of CBD and its major metabolites together with any estimates of PK parameters.
 
• Plasma and urine concentrations of THC and its major metabolites together with any estimates of PK parameters.
 
• Changes in plasma AED levels.
 
 
There are three treatments, so multiple significance testing will occur when making comparisons between the treatments; the major comparisons of interest are those between each of the GWP42003-P Dose Levels and placebo and, in particular, the 20 mg/kg/day Dose Level and placebo. A step down procedure will be used to control the type I error. The comparison of 20 mg/kg/day GWP42003-P and placebo will be tested first and only if this is statistically significant at the 5% level will the comparison of 10 mg/kg/day GWP42003-P and placebo be tested.
 
All statistical tests will be two-tailed and carried out at the 5% level of significance. All safety data will be summarized using appropriate statistical methods.

Sponsor	
GW Research Ltd          [name]          [name]          [name]          [name]          [name]          United Kingdom

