### **2.2 Secondary**

- To assess changes from baseline in convulsive and non-convulsive seizure frequency, duration, usage of rescue medication, number of inpatient hospitalizations due to epilepsy, sleep disruption, daytime sleepiness, quality of life, growth and development, and conduct behavioral and cognitive assessments in patients taking GWP42003-P as an adjunctive treatment, when compared with placebo.
- To determine the pharmacokinetics (PKs) of cannabidiol (CBD) and its major metabolites following single and multiple doses of GWP42003-P and to assess the presence of  $\Delta^9$ -tetrahydrocannabinol (THC) and its major metabolites in plasma and the presence of THC, CBD and their major metabolites in urine after multiple doses of GWP42003-P.
- To determine effects of GWP42003-P on plasma concentrations of concomitant antiepileptic drugs (AEDs), where available.
- To assess the safety of both GWP42003-P doses when compared with placebo.

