**PK:**

- The plasma concentrations of CBD and its major metabolites will be determined following single and multiple doses of GWP42003-P. The following PK parameters will be calculated from sparse sampling:
  - The concentration at each time interval ( $C_t$ ) of CBD and its metabolites.
  - Area under the plasma concentration curve ( $AUC_{0-t}$ ) from time zero to the last measurable concentration.

- Plasma concentrations of concomitant AEDs before and after treatment with GWP42003-P, where available.
- The plasma concentrations of THC and its major metabolites will be determined at a single time point (Visit 8, two to three hours post-dose) following multiple doses of GWP42003-P.
- The concentrations of THC, CBD, and their major metabolites will be determined in urine after multiple doses of GWP42003-P.

The safety profile of GWP42003-P compared with placebo will also be assessed at each Dose Level by measuring:

- AEs.
- Vital signs.
- Physical examination parameters.
- 12-lead Electrocardiogram (ECG).
- Clinical laboratory parameters.
- Columbia-Suicide Severity Rating Scale (C-SSRS) score.
- Cannabis Withdrawal Scale (CWS) or Pediatric Cannabinoid Withdrawal Scale (PCWS) score, as appropriate.
- Abuse liability.
- Effects on menstruation cycles (in females).

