### **13.6.5 Pharmacokinetics**

Plasma concentrations of CBD and its major metabolites will be summarized after the first dose of IMP at Visit 2 and at Visit 8, together with any estimates of PK parameters. Urine concentrations of CBD and its major metabolites will be summarized at Visit 8. Plasma and urine concentrations of THC and its major metabolites will be summarized at Visit 8.

Where available, plasma concentrations of concomitant AEDs will also be summarized pre-treatment with IMP (Visit 2) and at Visits 4, 6 and 8.

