### 2.2 Secondary

- To assess changes from baseline in non-convulsive seizure frequency, duration, usage of rescue medication, number of inpatient hospitalizations due to epilepsy, sleep disruption, daytime sleepiness, quality of life, growth and development, and conduct behavioral and cognitive assessments in patients taking GWP42003-P as an adjunctive treatment, when compared with placebo.
- To determine the PK of CBD and its major metabolites following single and multiple doses of GWP42003-P and to assess the presence of  $\Delta^9$ -tetrahydrocannabinol (THC) and its major metabolites in plasma and the presence of THC, CBD and their major metabolites in urine after multiple doses of GWP42003-P.
- To determine effects of GWP42003-P on plasma concentrations of concomitant AEDs, where available.

- To assess the safety of both GWP42003-P doses when compared with placebo.

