Table 14.8	Summary of Pediatric Cannabinoid Withdrawal Scale (4–17 Years)	Safety Analysis Set
Table 14.9	Summary of Plasma Concentrations of Concomitant Antiepileptic Drugs	Safety Analysis Set
Table 14.10	Summary of Caregiver Impression of IMP Palatability	Safety Analysis Set
Table 14.11	Summary of Study Medication Use and Behavior Survey	Safety Analysis Set
Table 14.12.1	Summary of Supplemental Drug Accountability Form	Safety Analysis Set
Table 14.12.2	Summary of Supplemental Adverse Event Form	Safety Analysis Set
Table 14.12.3	Summary of Site Classification Form	Safety Analysis Set

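### Concomitant AED levels are summarized by arm and visit but never paired with the Visit 2 value or compared with placebo, which falls short of the drug-interaction objective

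*SAP*

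**What the plan says.** The objective is the same in both documents. Protocol 2.2 has "To determine effects of GWP42003-P on plasma concentrations of concomitant antiepileptic drugs (AEDs), where available", and SAP 2.2 has "To determine effects of GWP42003-P on plasma concentrations of concomitant AEDs, where available".

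The endpoint is worded in two ways:
- The Statistical Considerations part of the protocol synopsis opens its list with "The following endpoints will be described and compared between treatment groups, using appropriate statistical methods" and includes "Changes in plasma AED levels" in it.
- Protocol 4.1.2, under PK, has "Plasma concentrations of concomitant AEDs before and after treatment with GWP42003-P, where available". SAP 3.3.2.2 repeats this endpoint.

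The analysis is narrower. Protocol 13.6.5 says that, where available, "plasma concentrations of concomitant AEDs will also be summarized pre-treatment with IMP (Visit 2) and at Visits 4, 6 and 8". SAP 5.7.2 says: "For each AED, plasma concentrations will be summarized by treatment group at each visit for patients in the safety analysis set". The only planned table is 14.9, titled "Summary of Plasma Concentrations of Concomitant Antiepileptic Drugs"; individual values go to Listing 14.10.

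**The concern.** The objective asks what the study drug does to the level of another drug in the same patient. The design provides for an answer: protocol 9.1.10 schedules a sample before IMP at Visit 2 and again at Visits 4, 6 and 8. The planned table treats Visit 2 as one more column and does not link it to the later values.

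Two features make this matter. First, sampling is conditional. Levels are reported where available, and a sample is taken only if the investigator judges the risk/benefit favorable (protocol 9.1.10). The patients summarized at Visit 8 need not be those summarized at Visit 2, so a shift between columns may reflect who was sampled. Second, AED doses are meant to stay stable, but protocol 8.2 allows adjustment when symptoms are thought to come from an interaction with the IMP. SAP 5.7.2 does not say how such patients are shown.

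At stake is whether the trial can report an interaction, or its absence, with a usable estimate from samples it already takes.

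**Working it through.** **1. What each place commits to**

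| Place | Visit summaries | Change or before/after | Comparison between groups |
|---|---|---|---|
| Protocol synopsis, Statistical Considerations | yes (described) | yes | yes |
| Protocol 4.1.2 and SAP 3.3.2.2 | – | yes | introduced as endpoints to be compared |
| Protocol 13.6.5 | yes | no | no |
| SAP 5.7.2 and Table 14.9 | yes | no | no |

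The SAP matches the last protocol row and misses the first two rows, one of which is its own endpoint list. The documents do not use the term within-patient. It is the natural reading of a change, and of levels before and after treatment.

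**2. Is the gap covered elsewhere in the SAP?**
- SAP 1 excludes only the PK of CBD and its metabolites, so AED levels remain in scope.
- Change from baseline is planned explicitly for laboratory parameters (5.6.3.1), vital signs (5.6.4.1), ECG (5.6.4.2), IGF-1 (5.6.4.5) and the PCWS (5.6.4.8), but not in 5.7.2.
- SAP 5.3 lets derived changes be added to listings as appropriate. It commits to no summary or comparison for AEDs.
- SAP 5.8 records other dropped or altered analyses and does not mention this one.

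**3. What pairing and adjustment could gain**

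The plan gives no figure to reproduce. Let r be the within-arm correlation, on the log scale, between the Visit 2 value and a later value in the same patients. The documents do not give r, so the values below are assumed. The SE factors are relative to an unadjusted arm comparison at the later visit:
- ANCOVA with the Visit 2 value as covariate: √(1 − r²)
- change from Visit 2, with equal SD at both visits: √(2(1 − r))

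| r (assumed) | ANCOVA | Change from Visit 2 |
|---|---|---|
| 0.3 | √0.91 = 0.95 | √1.4 = 1.18 |
| 0.5 | √0.75 = 0.87 | √1.0 = 1.00 |
| 0.7 | √0.51 = 0.71 | √0.6 = 0.77 |
| 0.9 | √0.19 = 0.44 | √0.2 = 0.45 |

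A simple change gains precision only when r exceeds 0.5. In large samples ANCOVA does not lose at any r, so it is the better basis for an arm comparison. The within-patient ratio is still worth showing as a description. Neither factor depends on sample size, so small AED subgroups do not make the relative gain larger.

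**4. How many patients**

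With 186 randomized 2:2:1:1 and placebo pooled, each group has 186 ÷ 3 = 62. An AED-specific comparison involves only users of that AED with paired samples, so it cannot exceed 62 against 62 and will usually be smaller. The documents give no counts by AED.

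**The case against.** The strongest reply is that SAP 5.7.2 does what protocol 13.6.5, the section that specifies this analysis, asks for. AED levels are also absent from the secondary endpoints listed for comparison in 13.6.3. A reader might infer that the SAP dropped a specified protocol analysis without declaring it. The documents do not support that: the protocol is inconsistent with itself, and the SAP followed the narrower text. What remains is that the narrower text does not deliver the objective or the listed endpoint.

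A reader might also infer that differences in AED dose and body weight confound the raw arm means. Arms are randomized, so these factors balance in expectation, and the Visit 2 column shows any chance imbalance. The comparison is noisier than it need be, not systematically biased by them. Nor do the documents say that dose and weight are the main sources of variation. The part that stands is that sampling can differ between visits and nothing adjusts for the Visit 2 level. That patients do differ between visits is a possibility the sampling rule allows, not an established fact.

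On size, the SAP plans no inference here, so no planned standard error would shrink; the factors above describe an analysis that would be added. A high r cannot be presumed, because samples are timed before IMP, while AED dose times are only recorded in the diary.

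Finally, this is a descriptive measure, reported where available, outside the primary and key secondary analyses. Paired values could be read off Listing 14.10. That limits the weight of the point but does not supply a summary.

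**Conclusion.** The point holds as a gap between a secondary objective and its planned analysis. The AED table agrees with protocol 13.6.5 but provides neither the change and comparison promised in the synopsis nor the before-and-after contrast in protocol 4.1.2 and SAP 3.3.2.2. The loss is mainly in precision and interpretability. If r is between 0.5 and 0.9, baseline adjustment would multiply the standard error by about 0.87 to 0.44; the true r is unknown, and the gain is slight at low r (0.95 at 0.3).

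A reader might infer that the analysis should be confined to patients whose AED dose did not change. That would select on a post-randomization event which protocol 8.2 ties to suspected interaction. It could remove the patients with the largest effects and bias the estimate toward no effect. A call for AED metabolites also has no basis in the documents, which name metabolites only for CBD and THC.

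The primary and key secondary analyses are unaffected. The change is worth making because the samples are already planned.

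**What to change.** In SAP 5.7.2 and Table 14.9, for each AED assayed:
1. Add the within-patient ratio to Visit 2 at Visits 4, 6 and 8 by arm, in patients with paired samples, with the number of pairs at each visit.
2. Where numbers allow, add the active-to-placebo (pooled) geometric mean ratio with 95% CI, from ANCOVA on log concentration with log Visit 2 concentration as covariate. State beforehand the minimum number of pairs for fitting the model.
3. Use all paired patients for the main summary, flag those whose AED dose changed, and show unchanged-dose patients only as a supportive analysis.

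Align the synopsis, protocol 13.6.5, SAP 3.3.2.2 and SAP 5.7.2 so that they describe the same analysis. If the sponsor prefers visit summaries alone, record in SAP 5.8 that the change and comparison will not be done, and why.

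The cost is SAP wording and a few table rows. The AED samples and the recording of AED changes are already in the protocol. The drawback is that numbers for some AEDs will be small and their intervals wide.
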